1.0 Objectives

- 1.1 To determine the complete remission (CR) rate, remission duration, leukemia-free survival, and survival in patients ≥ 70 years with previously untreated AML with 4 different SGI-110 single agent and SGI-110 based combination regimens.
- 1.2 To determine the safety profile and tolerability of the 4 SGI-110 single agent and SGI-110 based combination regimens in patients ≥ 70 years of age with previously untreated AML.

2.0 Background

2.1 The Diseases

Acute myeloid leukemia (AML) accounts for approximately 25% of all cases of leukemia diagnosed in the Western hemisphere. It is a clonal myelopoietic stem cell disorder characterized by the accumulation of neoplastic cells in the bone marrow and in the peripheral circulation. Age-adjusted incidence ranges from 1 per 100,000 in people < 20 years to 10 per 100,000 in the elderly. Current induction chemotherapy protocols combining cytarabine and an anthracycline administered as first-line treatment induce complete remissions in a majority (55% to 75%) of patients. Standard consolidation therapy with high doses of cytarabine leads to improved survival. Between 50% and 70% of patients, however, can be expected to relapse, so that only about 30% attain long-term disease-free survival.

Age is a major factor that determines the prognosis of patients with untreated AML. The treatment of acute myeloid leukemia (AML) in older patients has not improved significantly in recent years when compared with the considerable progress that has been made in younger patients (1-3). AML occurring in patients ≥ 60 years of age continues to be associated with an extremely poor prognosis. Using a standard induction combination such as the "3+7" regimen (ara-C plus an anthracycline), the complete remission (CR) rate is 40% to 50%, the mortality 20% to 40%, and remission durations are usually transient and rarely last more than 12 months. The median time from treatment with the "3+7" regimen to death is 5 to 10 months and less than 10% of patients stay in remission at 3 years (4). Patients who are ≥ 70 years of age in particular tolerate 3+7 induction regimen very poorly with even worse results [20]. The reasons for this difference in outcome when compared to younger patients are multiple. Differences in the biology of AML in older patients is reflected by a higher proportion of patients with an unfavorable karyotype, a higher rate of primary drug resistance associated with overexpression of P-glycoprotein (P-gp), and an increased frequency of disease evolution from a preexisting and at time probably unrecognized myelodysplasia. Poorer tolerance of combination chemotherapy regimens leads to the use of less intensive treatment protocols (5). It is clear that several aspects of therapy in this group of patients require improvement. The development of new and effective anti-AML agents, however, remains a cornerstone of the continued efforts to improve the outcome of poor-prognosis patients. As the principal cause of treatment failure in older patients is resistant AML (manifested by short CR durations or failure to enter CR), investigational strategies should focus primarily on this problem and the introduction of new agents is warranted.

2.2 The Treatment - SGI-110 4-arm study

For the most updated SGI-110 clinical data, please refer to the most recent SGI-110 Investigators' Brochure.

SGI-110 is a novel second generation hypomethylating agent which has been rationally synthesized to increase the half-life of its metabolite, decitabine, and to improve on the hypomethylation efficacy. SGI-110 has undergone completed Phase I studies. Phase 2 studies using SGI-110 60mg/m² versus 90mg/m² daily for 5 days are ongoing in newly diagnosed MDS and AML and in MDS salvage. SGI-110 60mg/m² daily x 10 is undergoing evaluation in AML salvage. The results so far appear very encouraging demonstrating longer half-life of the decitabine metabolite, better hypomethylation capacity with SGI-110 compared with previous data with Dacogen (commercial decitabine), significant anti-MDS and anti-AML efficacy, and minimal side effects (6,7).

In a Phase I study, 78 patients (64 AML, 14 MDS) were enrolled in the dose escalation part: 44 patients in the daily x 5 regimen and 34 in the weekly x 3 regimen. There median age was 69 years. Median number of prior regimens was 3.

The PK profile demonstrated efficient conversion of SGI-110 to decitabine as predicted from the SGI-110 rational design, resulting in longer SGI-110 exposure window (beyond 8 hours) compared to Dacogen IV (3-4 hours). At SGI-110 dose range of 60-125 mg/m², observed mean decitabine AUCs (88-231 ng*hr/mL) reach or exceed the therapeutic range seen with 20 mg/m² Dacogen IV (115 ng*hr/mL) while achieving only a small fraction of the Cmax (26-64 ng/mL vs 146 ng/mL for Dacogen IV). The effective half-life for decitabine after subcutaneous SGI-110 injection appeared to be prolonged (up to 4-fold or ~2.4 hours) compared to Dacogen IV (0.58 hrs). SGI-110 exposures (AUC) increased in a dose proportional manner regardless of the regimen and no accumulation was observed.

Dose-related LINE-1 hypomethylation was observed in patients treated with the daily regimen between 18 and 60 mg/m²; a plateau in maximum average hypomethylation (~25%) was evident at higher daily doses (90-125 mg/m²) and therefore the BED for the daily x 5 schedule is established at 60 mg/m². The 25% average hypomethylation of LINE-1 compares favorably with that observed historically after Dacogen IV at the dose of 20 mg/m² daily x 5. The extent of LINE-1 hypomethylation after weekly x 3 SGI-110 was inferior as the maximum average hypomethylation plateaued at ~8% from baseline.

Starting at 36 mg/m² daily and 60 mg/m² weekly (44 AML, and 7 MDS patients), clinical responses were observed: 2 CRs, 1 CRp, and 1 CRI in heavily pretreated AML patients; 1 mCR and 1 HI in MDS patients previously treated with azacitidine. All responses were in patients who achieved >10% LINE-1 hypomethylation. The most common adverse events (AEs), regardless of relationship to SGI-110, were diarrhea (21%), febrile neutropenia (17%), fatigue/injection site pain/nausea at 15% each. The most common drug-related AEs were injection site pain (15%), fatigue (8%), nausea (6%), and thrombocytopenia (5%). The MTD was not reached with the weekly regimen up to 125 mg/m² weekly x 3. With the daily regimen, 125 mg/m² daily x 5 resulted in 2 dose-limiting toxicities (DLTs) of febrile neutropenia in 3 MDS patients (1 associated with bacteremia, and the other with sepsis and thrombocytopenia Grade 4) while none of the 9 patients with AML had DLT at that dose (14). Since the abstract publication, maximum hypomethylation was noted at the 60mg/m² dose, while clinical MTD was defined at 90mg/m² dose. Therefore the Phase II study proceeded to compare 60 versus 90mg/m² daily for 5 days in newly diagnosed MDS and AML. A further arm investigated SGI-110 60mg/m² daily x 10 days in AML salvage. Finally SGI-110 60mg/m² daily x 5 is being evaluated in patients with MDS and progression on azacitabine/SGI-110 therapy (6).

The Phase II randomized study of the biologic effective dose 60mg/m² daily x 5 and clinical Phase II dose 90mg/m² daily x 5 is ongoing. As of June 30, 2013, sixty-seven patients (50 relapsed/refractory AML, 17 treatment naïve elderly AML) were treated and had a minimum follow up of 3 months. Patients were randomized to either 60 mg/m² dose (32 patients) or 90 mg/m² dose (35 patients). The median age was 66 years (range, 22-84), 69% were male, and ECOG PS of 0/1/2 was reported in 11/47/9 patients respectively. Median number of prior regimens was 2

(range, 0–10). Patients' characteristics were well balanced between the 2 dose groups. The primary endpoint of overall remissions (CR, CRp, or CRi) was observed in 17/67 patients (25% with 95% CI, 16–37%). There were 8 complete remissions (CR, CRp, or CRi) in 50 patients with relapsed/refractory AML (16% with 95% CI, 7–29%); and 9 complete remissions (CR, CRp, or CRi) in 17 treatment-naïve elderly AML patients (53% with 95% CI, 28–77%). Five patients (4 relapsed/refractory, and one treatment-naïve elderly AML) subsequently received a stem cell transplant. There was no difference in the complete remission rate between 60 and 90 mg/m² doses (8 remissions in 32 patients at 60 mg/m², and 9 remissions in 35 patients at 90 mg/m²). LINE-1 DNA methylation data before and after treatment was available in 50 (75%) patients enrolled. LINE-1 demethylation \geq 10% post treatment was observed in 83% and 78% in the 60 mg/m² and 90 mg/m², respectively. The median maximum LINE-1 demethylation for responders is 25% as compared to 19% for non-responders. The most common adverse events (AEs) regardless of relationship to SGI-110 \geq Grade 3 include febrile neutropenia, thrombocytopenia, anemia, leukopenia, neutropenia, and pneumonia. The 90 mg/m² dose showed a greater frequency of Grade 3/4 related AEs \geq 10% (anemia, febrile neutropenia, leukopenia, neutropenia, and thrombocytopenia) compared to the 60 mg/m² dose (7).

2.3 Rationale for the Proposed Regimen in Elderly AML

Up to 50 patients older than age 65 with newly diagnosed AML were treated in the previously described Phase II studies under 2.2. The early results are impressive in terms of CR and marrow CR rates. In our institutional experience, 9 of the first 12 patients treated achieved remissions. This is significant in this elderly AML population. We are therefore proposing an investigator initiated IND study to gain further experience with different SGI-110 regimens. This will help in the Phase III design of the potential FDA pivotal trial which will evaluate SGI-110 based therapy versus best standard of care in patients who cannot tolerate intensive chemotherapy. We will restrict the evaluation in the study to patients 70 years or older, since there is little argument that such patients do not benefit from intensive anti-AML therapy. Since we do not know whether 5 or 10 days of hypomethylator therapy is better, we propose to include 2 arms, one using single-agent SGI-110 60mg/m² SQ daily x 5, and the second using SGI-110 60mg/m² SQ daily x 10. We wish also to explore, in this pilot experience SGI combinations. Anthracyclines are historically effective in AML; therefore a third arm will evaluate SGI-110 60mg/m² SQ daily x 5 with idarubicin at the low-dose 6mg/m² daily x 2. Finally, cladribine, an old drug with single-agent efficacy in AML, was found to be an effective hypomethylating agent. Therefore combining SGI-110 with cladribine at low-doses may improve the anti-AML and hypomethylation efficacy. The fourth arm will combine SGI-110 60mg/m² SQ daily x 5 with cladribine 3mg/m² daily x 5.

2.4 Update of January 27, 2017

As of February 2017, 34 patients have been treated on study. The complete response in the 4 treatment arms are as follows: 4 out of 8 patients responded in the SGI-110 for 5 days arm; 5 out of 9 patients responded in the SGI-110 for 10 days arm; 7 out of 8 patients responded in the SGI+idarubicin arm and 3 out of 9 patients responded in the SGI+cladribine.

In addition, Astex, the sponsoring company, conducted a separate multi-institutional study of SGI-110 60mg/m² for 5 and 10 days in older patients with newly diagnosed AML who were not candidates for intensive chemotherapy (8). A total of 103 patients were treated, 51 patients were treated on the 5-day and 52 patients were treated on the 10-day regimens. The characteristics of the 2 study groups were well-balanced. Overall the CR rates were 19/51 = 37% on the 5-day regimen and 16/52 = 31% on the 10-day regimen. The overall response rates were 57% and 48%, respectively. The median survival were 10.5 months on the 5-day regimen and 9.5 months on the 10-day regimen ($p=0.70$). Side-effects, including myelosuppression, were similar in the 2 study groups. The 60-days all-cause mortality was also similar between the two study groups.

The study concludes that both schedules (SGI-110 given in 5-day and SGI-110 given in 10-day) were similar (8).

Based on the above findings, and after discussion with the Biostatistical collaborators, [name] and [name], it was decided to close the 2 arms of SGI-110 for 10 days (based on the Astex study) and SGI-110 + cladribine (low CR rate), and continue the study, with the same Bayesian statistical design, only in the 2 arms of SGI-110 for 5 days and SGI-110 + idarubicin.

3.0 Background Drug Information

3.1 SGI-110

Further information is available in the Investigator Brochure.

3.1.1 General Information

The active metabolite of SGI-110 (2'-deoxy-5-azacytidylyl-(3'→5')-2'-deoxyguanosine sodium salt), a dinucleotide, is decitabine. SGI-110 is resistant to modification by cytidine deaminase, a common pathway of decitabine metabolism and deactivation. The molecular weight of SGI-110 and decitabine are 580 Da and 228 Da, respectively. Therefore, the molar equivalent dose of 1 mg of decitabine is approximately 2.5 mg of decitabine. SGI-110's activity was demonstrated with the same preclinical pharmacodynamic assays used to demonstrate decitabine's efficacy e.g., re-expression of p15, p16, and MLH1 and induction of fetal hemoglobin, *in vivo*. In xenograft studies, SGI-110 demonstrates promising preclinical activity in both hematologic and solid tumors.

[figure not shown]
In vitro evidence suggests that SGI-110 has a longer half-life than decitabine in the presence of cytidine deaminase. Exploratory preclinical studies demonstrate that unlike decitabine, SGI-110 can suppress the polycomb repressor complex 2 which is involved in silencing tumor suppressor genes. These promising observations suggest that SGI-110 has improved pharmaceutical properties and biological activities that expand on decitabine's current clinical utility. SGI-110 has shown to be better tolerated in mice than decitabine and is as effective *in vivo* in inducing p16 expression, reducing DNA methylation at the p16 promotor region, and retarding EJ6 human bladder cancer tumor growth in athymic mice.

3.1.2 Summary of Nonclinical Data

a. In Vitro Pharmacology

The ability of SGI-110 to change global methylation status was tested by determining the methylation level of long interspersed nucleotide element-1 (LINE-1) and p16 sequences (Figure 1). Repetitive DNA elements, such as LINE-1 retro transposable elements, serve as useful markers of genome-wide methylation changes and have previously been shown to be demethylated upon treatment with SGI-110 or decitabine (5-Aza-CdR). Both azacitidine and decitabine by itself have low objective response rates.

[figure not shown]
Figure 1: Effects of SGI-110 (filled bars) and decitabine (open bars) on LINE-1 and p16 Gene Methylation Levels in T-24 and HCT116 Cell Lines

In both T-24 and HCT116 cells, the decrease in the level of methylation was dose-dependent and comparable for SGI-110 and decitabine after 0.1 μ M and 1 μ M treatment (Figure 1). In the figure noted above and any subsequent places in this document, SGI-110 is the same as SGI-110. At 10 μ M concentrations, only a small decrease in methylation was noted, probably due to side effects of high drug concentrations. In fact, 10 μ M treatments may be too cytotoxic for effective demethylation to take place as the plating efficiency of T-24 cells indicates. It is well-established that the cytotoxic dose of these demethylating agents is not ideal for optimal epigenetic therapy, since these drugs inhibit DNA methylation best at low doses in cell lines as well as in the clinic.

Next, the changes in a methylation-silenced tumor suppressor gene, p16 were assayed in both cancer cell lines.

Figure 2: Effects of SGI-110 (filled bars) and decitabine (open bars) on p16 Gene: Expression Levels in T-24 (left) and HCT116 (right) Cells

[figure not shown]
As shown in Figure 2, untreated T-24 bladder carcinoma cells do not express p16, and dose dependent

increases in p16 expression were observed after 6 days of continuous treatment with SGI-110 or decitabine. After HCT116 colorectal carcinoma cells were treated for six days, a dose dependent increase in p16 expression was observed with both SGI-110 and decitabine.

In Vivo Pharmacology

The efficacy and safety of SGI-110 was evaluated in several solid tumor models and HL-60 promyelocytic leukemia in comparison to equivalent doses of decitabine (Astex Pharmaceuticals, Inc., data on file). Female nu/nu mice were implanted subcutaneously with HL-60 cells. Animals with exponentially growing tumors were randomized into 5 groups of 8 animals each to include vehicle, SGI-110 5 mg/kg administered subcutaneously every 7 days and 2.5 mg/kg administered intraperitoneally Monday to Friday. Equivalent doses and schedules of decitabine 12.2 mg/kg and 6.1 mg/kg, respectively, were administered subcutaneously for comparison. Results from this study are shown in Table 1 and Figure 3. Both SGI-110 and decitabine demonstrated equivalent antiproliferative activity when administered subcutaneously. When dosed intraperitoneally, SGI-110 seemed to have a greater effect but at the expense of higher toxicity as evidenced by more weight loss and death of 1 animal in the decitabine group.

Figure 3: SGI-110 and decitabine Activity and Body Weight Loss in HL-60 Promyelocytic Leukemia

C. General Safety (Cardiac, CNS, and Respiratory)

SGI-110 was tested to examine the in vitro effects on the human ether-a-go-go related gene (hERG) potassium channel current. Whole cell patch clamp recordings were made on human embryonic kidney (HEK293) cells that were stably transfected with hERG cDNA. SGI-110 was tested at 10 μ M and 300 μ M.

SGI-110 inhibited hERG current by $1.4 \pm 0.3\%$ (mean \pm SEM) at 10 μ M and by $1.0 \pm 1.3\%$ 300 μ M. The half maximal inhibitory concentration (IC₅₀) for the inhibitory effect of SGI-110 on hERG current was not calculated but was estimated to be greater than 300 μ M.

The potential neurobehavioral toxicity of SGI-110 was studied after a single subcutaneous dose of SGI-110 (0, 5, 10, and 20 mg/kg) in 2 repeat dose GLP toxicology studies in rats. Functional Observational Battery (FOB) evaluations were conducted on 10 main study animals/group pre-dose (Day -1) and 1 hour post-dose on Day 1 of the study [23] [24]. There were no SGI-110 related changes in any of the FOB measurements in either study. The unobserved-adverse-effect level (NOAEL) of SGI-110 on neurobehavioral function is 30 mg/kg.

The potential effects of SGI-110 on respiratory function were studied in a GLP study in rats. Pulmonary function (respiratory rate, tidal volume, and minute volume) were monitored continuously on 8 animals/sex/group for at least 1 hour pre-dose and at least 4 hours post dose. Test article or vehicle was administered to all groups via a single subcutaneous injection (0, 15, 30, and 60 mg/kg) SGI-110 did not produce mortality and had no effect on clinical signs, respiratory rate, tidal volume, and minute volume. With respect to the basic pulmonary endpoints evaluated in this study, a no-observed-effect-level (NOEL) of at least 60 mg/kg has been established for SGI-110.

3.1.3 Risks of SGI-110 single agent and combination with idarubicin

For the most up to date clinical safety information, please refer to the most recent Investigators' Brochure.

The most common risks of SGI-110 are similar to decitabine. These include myelosuppression (neutropenia, febrile neutropenia, thrombocytopenia, and anemia) and its consequences such as fever, infection, sepsis, bacteremia, or bleeding. While in GLP toxicity studies with SGI-110 subcutaneous injections, no adverse local site reactions were noted in the multiple-dose rat and rabbit studies, clinical data indicate injection site pain, irritation, or inflammation in approximately 15% of patients. Local pain seems to be ameliorated by the use of ice packs before or after injection, injecting SGI-110 slowly instead of a push, and carefully avoiding intradermal injections.

Risks of idarubicin described below in the subsequent sections.

There is no available clinical data for the combination of SGI-110 with idarubicin but the only overlapping toxicity of all 3 agents is myelosuppression which should be well-monitored and managed during the first cycle. This is also why the study proposes the use of only a fraction of the commercially and clinically full doses of idarubicin in combination with the full dose of SGI-110.

3.1.4 Potential Benefits of SGI-110

Astex Pharmaceuticals has synthesized more stable and potent inhibitors of DNA methylation than decitabine, and demonstrated that short oligonucleotides containing an azapyrimidine effectively inhibit DNA methylation in living cells. SGI-110 was synthesized by coupling decitabine and guanosine into a dinucleotide in an attempt to improve the biological stability and thereby increase the in vivo efficacy of decitabine. Unlike decitabine, SGI-110 initially is resistant to deamination by cytidine deaminases until it is converted into decitabine as a result of cleavage of the phosphodiester linkage by phosphodiesterases. As such, decitabine is the active metabolite of SGI-110. SGI-110 is a new chemical entity that may possess enhanced pharmacokinetic or pharmacodynamic properties compared to SGI-110.

The activity of SGI-110 was demonstrated with the same preclinical pharmacodynamics assays used to demonstrate the activity of decitabine, e.g., re-expression of p15, p16, and MLH1 and induction of fetal hemoglobin, in vivo. In vivo data demonstrate interspecies differences with respect to absorption, distribution, and conversion to decitabine. In xenograft studies, SGI-110 demonstrates promising nonclinical activity in hematologic malignancy and solid tumors.

As such, SGI-110 is an agent that holds promising activity in hematological malignancies given decitabine's proven activity in MDS and AML. The dosage form of SGI-110 developed for use in this study as a subcutaneous injection has the potential for a more sustained release effect compared to an IV short infusion which, in addition of being more convenient, may prolong efficacy, lower toxicity and change the PK in a beneficial way.

3.2 Idarubicin

Idarubicin is commercially available. Please see package insert for further information.

Synonyms 4-Demethoxydaunorubicin; 4-DMDR, Idarubicin Hydrochloride, IDR: IMI30; NSC-256439, SC 33428

Use Treatment of acute leukemias (AML, ANLL, ALL), accelerated phase or blast crisis of chronic myelogenous leukemia (CML), breast cancer

Contraindications Hypersensitivity to idarubicin, other anthracyclines, or any component of the formulation; bilirubin >5 mg/dl; pregnancy

Warnings/Precautions The U.S. Food and Drug Administration (FDA) currently recommends that procedures for proper handling and disposal of antineoplastic agents be considered. Can cause myocardial toxicity and is more common in patients who have previously received anthracyclines or have pre-existing cardiac disease; reduce dose in patients with impaired hepatic function.

The Investigator will ensure that any used and unused vials of study drug and other study material will be destroyed or returned to the Sponsor on completion of the study.

Adverse Reactions

>10%

Cardiovascular: Transient EKG abnormalities (supraventricular tachycardia, S-T wave changes, atrial or ventricular extrasystoles); generally asymptomatic and self-limiting. Congestive heart failure, dose-related. The relative cardiotoxicity of idarubicin compared to doxorubicin is unclear. Some investigators report no increase in cardiac toxicity at cumulative oral idarubicin doses up to 540 mg/m²; other reports suggest a maximum cumulative intravenous dose of 150 mg/m².

Central nervous system: Headache

Dermatologic: Alopecia (25% to 30%), radiation recall, skin rash (11%), urticaria

Gastrointestinal: Nausea, vomiting (30% to 60%); diarrhea (9% to 22%); stomatitis (11%); GI hemorrhage (30%)

Genitourinary: Discoloration of urine (darker yellow)

Hematologic: Myelosuppression, primarily leukopenia; thrombocytopenia and anemia. Effects are generally less severe with oral dosing

Nadir: 10-15 days

Recovery: 21-28 days

Hepatic: Elevations of bilirubin and transaminases (44%) 1% to 10%

Central nervous system: Seizures

Neuromuscular & skeletal: Peripheral neuropathy <1%: Hyperuricemia

Overdosage/Toxicology Symptoms of overdose include severe myelosuppression and increased GI toxicity. Treatment is supportive. It is unlikely that therapeutic efficacy or toxicity would be altered by conventional peritoneal or hemodialysis.

Drug Interactions Patients may experience impaired immune response to vaccines; possible infection after administration of live vaccines in patients receiving immunosuppressants

Stability Store intact vials of solution under refrigeration (2°C to 8°C/36°F to 46°F); protect from light. Solutions diluted in D₅W or NS for infusion are stable for 4 weeks at room temperature and 7 days under refrigeration.

Mechanism of Action Similar to doxorubicin and daunorubicin; inhibition of DNA and RNA synthesis by intercalation between DNA base pairs

Extravasation management: Topical cooling may be achieved using ice packs or cooling with circulating ice water. Cooling of site for 24 hours as tolerated by the patient. Elevate and rest extremity 24-48 hours, then resume normal activity as tolerated. Application of cold inhibits vesicant's cytotoxicity. Application of heat can be harmful and is contraindicated. If pain, erythema, and/or swelling persist beyond 48 hours, refer patient immediately to plastic surgeon for consultation and possible debridement.

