4.0 Patient Eligibility

Inclusion:

- 4.1 Previously untreated AML patients, except those who have received prior therapy with hydroxyurea, single agent chemotherapy (e.g. decitabine), hematopoietic growth factors, biological or targeted therapies are allowed.
- 4.2 Age \geq 70 years.
- 4.3 ECOG performance status \leq 2.
- 4.4 Sign a written informed consent form.
- 4.5 Adequate liver function (total bilirubin \leq 2mg/dL, SGPT or SGOT \leq x 4 ULN) and renal function creatinine clearance of \geq 50 mL/min (estimated by the Cockroft-Gault [C-G] formula).
- 4.6 Male patients must use an effective contraceptive method during the study and for a minimum of 8 weeks after study treatment.
- 4.7 Baseline LVEF $>/=$ 40%.

Exclusion:

- 4.8 Patients with \geq NYHA grade 3 heart disease as assessed by history and/or physical examination.

- 4.9 Patients who received more than one full course of prior hypomethylating agents azacitidine or decitabine
- 4.10 Have any other severe concurrent disease, or have a history of serious organ dysfunction or disease involving the heart, kidney, liver, or other organ system that may place the patient at undue risk to undergo treatment.
- 4.11 Patients with a systemic fungal, bacterial, viral, or other infection not controlled (defined as exhibiting ongoing signs/symptoms related to the infection and without improvement, despite appropriate antibiotics or other treatment).
- 4.12 Pregnant or lactating patients.
- 4.13 Any significant concurrent disease, illness, or psychiatric disorder that would compromise patient safety or compliance, interfere with consent, study participation, follow up, or interpretation of study results.
- 4.14 Any concurrent malignancy (with the exception of exclusion # 4.15)
- 4.15 Exceptions to # 4.14: a) Patients with treated non-melanoma skin cancer, in situ carcinoma, or cervical intraepithelial neoplasia, regardless of the disease-free duration, are eligible for this study if definitive treatment for the condition has been completed; b) Patients with organ-confined prostate cancer with no evidence of recurrent or progressive disease based on prostate-specific antigen (PSA) values are also eligible for this study if hormonal therapy has been initiated or a radical prostatectomy has been performed.

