5.0 Treatment Plan

5.1 Schedule

Patients are randomized between 2 treatment arms:

Induction:

- A) SGI-110 60mg/m² subcutaneously (SQ) daily x 5
- B) SGI-110 60 mg/m² SQ daily x 5 + idarubicin 6mg/m² IV daily x 2

Cycles will be repeated every 4 to 6 weeks or longer as indicated by leukemia recurrence or recovery of normal hematopoiesis. Since efficacy from epigenetic treatment with agents such as SGI-110 may take longer to manifest, it is recommended that patients receive at least 2 courses of the above regimens regardless of their response.

If a patient does not achieve a CR or CR_i after a maximum of 3 induction courses, the patient will be taken off study unless the patient is deriving clinical benefit at which time continuation of protocol therapy will be allowed with prior PI approval.

Maintenance:

Patients who achieve a CR or CR_p during induction may receive up to 24 months of maintenance therapy every 4 to 8 weeks. The maintenance arm will be the same as the induction arm e.g. patients who are induced on SGI-110 + idarubicin are also maintained with SGI-110 + idarubicin.

- A) SGI-110 60mg/m² SQ daily x 5**
- B) SGI-110 60mg/m² SQ daily x 5 + idarubicin 6 mg/m² IV on Day 1**

- Patient may receive follow up laboratory tests from their local physician.
- All protocol-specific treatment decisions will be made by MD Anderson physician.
- The PI/treating physician must review all outside lab results, determine the clinical significance and sign/date the report.

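### Near full dose at close to 4-week intervals, arm B maintenance can pass the only cumulative IV idarubicin figure the protocol cites, and no rule totals or acts on cumulative dose

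*Combined protocol and SAP*

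**What the plan says.** **Drug information (3.2).** The warnings state: "Can cause myocardial toxicity and is more common in patients who have previously received anthracyclines or have pre-existing cardiac disease". The cardiovascular reactions include "Congestive heart failure, dose-related". The protocol then calls idarubicin's cardiotoxicity relative to doxorubicin unclear. It sets reports of no increase at oral totals up to 540 mg/m² against the remark that "other reports suggest a maximum cumulative intravenous dose of 150 mg/m²". Arm B gives idarubicin intravenously.

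**Schedule (5.1, arm B).** Each induction course includes "idarubicin 6mg/m² IV daily x 2", and at least 2 courses are recommended. A patient without CR or CRi "after a maximum of 3 induction courses" leaves the study, unless there is clinical benefit and the principal investigator approves continuation. Responders "may receive up to 24 months of maintenance therapy every 4 to 8 weeks", with 6 mg/m² IV idarubicin on day 1 of each arm B cycle. Section 5.1 adds: "The maintenance arm will be the same as the induction arm".

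**Cardiac provisions.**
- Entry: baseline LVEF of at least 40% (4.7); NYHA grade 3 or higher excluded (4.8); patients with a "history of serious organ dysfunction or disease involving the heart, kidney, liver, or other organ system" excluded where this may put them at undue risk (4.10).
- On treatment: LVEF following induction in patients receiving idarubicin (5.2), and every 3 to 4 cycles, qualified by clinical indication (7.0).
- Action: reduction to 4 and then 3 mg/m² for grade 3-4 drug-related non-hematologic toxicity or prolonged myelosuppression. Idarubicin may be reduced without SGI-110, and its days may be cut with the principal investigator's approval (all 5.2). Therapy may be stopped on the physician's judgement (9.1) or for unacceptable toxicity (9.3).

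**The concern.** The protocol describes a dose-related cardiac risk and cites one cumulative figure for the route it uses, yet its schedule can take a patient past that figure without any deviation. Section 3.1.3 defends the combination on the ground that each idarubicin dose is a fraction of the usual one and that myelosuppression will be watched in the first cycle. That does not address what accumulates over two years.

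Patients are at least 70 and may enter with an LVEF of 40%. Eligibility says nothing about earlier anthracycline, which 3.2 names as raising the risk and which would add to the on-study total. The stake is the cardiac safety of a few long responders.

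**Working it through.** The protocol gives no cumulative total for arm B, so there is no stated figure to reproduce. The 150 mg/m² is a literature value whose inputs are not shown.

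**Inputs (5.1, 5.2).** Induction: 6 × 2 = 12 mg/m² per course, with k = 1, 2 or 3 courses. Maintenance: 6 mg/m² per cycle for n cycles. Assumption: 24 months = 104 weeks.

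**Formula.** Total = 12k + 6n.

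| Maintenance | n | k = 1 | k = 2 | k = 3 |
|---|---|---|---|---|
| every 4 weeks | 26 | 168 | 180 | 192 |
| monthly | 24 | 156 | 168 | 180 |
| every 5 weeks | 20 full cycles | 132 | 144 | 156 |
| every 5 weeks | 21 starts | 138 | 150 | 162 |
| every 6 weeks | 17 full cycles | 114 | 126 | 138 |
| every 6 weeks | 18 starts | 120 | 132 | 144 |
| every 8 weeks | 13 | 90 | 102 | 114 |
| every 4 weeks, 4 mg/m² throughout | 26 | 116 | 128 | 140 |

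The last row uses 12k + 4 × 26.

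**When 150 is passed.** The smallest n with 12k + 6n > 150 is 24, 22 or 20 (total 156 each time). At 4-week intervals that cycle starts in week 4(n − 1) = 92, 84 or 76, about month 21, 19 or 17.5.

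**How narrow the case is.**
- Mean interval: cycle n follows n − 1 gaps, so it can be at most 104/23 = 4.5, 104/21 = 5.0 or 104/19 = 5.5 weeks.
- Omitted doses: 12k + 6(26 − s) > 150 allows at most s = 2, 4 or 6 omissions.
- Lasting reduction to 4 mg/m² after a full-dose cycles: 12k + 6a + 4(26 − a) > 150 requires a > 23 − 6k. A reduction after 17, 11 or 5 full-dose cycles or fewer therefore keeps the total at or below 150.

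**Beyond 3 induction courses.** Section 5.1 does not state a different dose for continued therapy. If it stays at 12 mg/m², the 13th course reaches 12 × 13 = 156.

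**LVEF checks before the crossing.** Counting induction, (n − 1) + k = 24, 23 or 22 cycles come first. One check every 4 cycles gives 6, 5 or 5; one every 3 gives 8, 7 or 7. That is about 5 to 8 checks, plus baseline, if 7.0 is followed.

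**Effect of a stop at 150.** The last permitted idarubicin dose is at maintenance cycle 23, 21 or 19 (total exactly 150). That forgoes 3, 5 or 7 of 26 doses, or 1, 3 or 5 of 24.

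**The case against.** **The 150 figure is not a protocol limit.** Section 3.2 presents it as one side of an unsettled literature, gives no population or event rate behind it, and points to a package insert not reproduced here. This stands. A reader might infer that the schedule breaks the protocol's own rule; it does not. The sponsor may hold that another limit is right, and the change proposed allows for that.

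**Cardiac monitoring already exists.** This also stands. A reader might infer that arm B has no cardiac safeguard or that nothing prompts a check; sections 4.7, 4.8, 4.10, 5.2, 7.0 and 9 rule that out. At a fixed dose, LVEF every 3 to 4 maintenance cycles is a check about every 18 to 24 mg/m². But the timing is left to judgement, no on-treatment LVEF threshold or resulting action is given, and the reduction triggers are toxicity or prolonged myelosuppression that has already occurred.

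**Few patients will get there.** Section 2.4 reports a median survival of 10.5 months on single-agent 5-day SGI-110 in a separate study, and the count recovery that 5.2 requires before each cycle tends to lengthen intervals. This limits the importance of the point but does not remove the gap. It does defeat any inference that a typical arm B patient would pass 150.

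**Clinicians can already drop idarubicin.** They can, under 5.2 and 9.1. Those provisions depend on someone noticing the total, while the default in 5.1 is to continue.

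**Conclusion.** The concern holds as a late corner case. At or near full dose with intervals close to 4 weeks, arm B reaches 168 to 192 mg/m² IV over 26 maintenance cycles (156 to 180 over 24), which exceeds the cited figure by 18 to 42 mg/m² (6 to 30). With 3 or fewer induction courses, 150 is not passed at 6- to 8-week intervals or at 4 mg/m² throughout maintenance. Courses beyond 3 can also lead past it.

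This rests on 24 months being about 104 weeks, few omitted or reduced doses, and no earlier anthracycline; any earlier exposure would bring the crossing forward. The documents do not say how many patients would stay on maintenance that long, so the statement that they will be few is a judgement. The complete remission endpoint, sample size and stopping rules are unaffected. The point is worth considering as a safety improvement; it does not count against the main design.

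**What to change.** Add to 5.1 and 5.2: before every arm B course (induction, continued therapy beyond 3 courses, and maintenance), total the IV idarubicin given on study and take account of any prior anthracycline found in the 6.0 history. If the next dose would take the total above 150 mg/m², omit idarubicin, continue SGI-110 alone, and analyse the patient in arm B. Word this as an exception to the sentence that ties maintenance to the induction arm. If the sponsor prefers another limit, state that value in the rule with the reason. The documents give no conversion between anthracyclines, so the rule should also say how prior exposure counts.

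The cost is a few sentences and one running total per arm B patient. Section 5.2 already permits reducing idarubicin alone. The downside is that a few long responders stop idarubicin late, which slightly mixes the arm B regimen when remission duration and survival are read.
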